#### **7.4.3 Clinical Laboratory Assessments**

Blood and urine samples will be collected for the following clinical laboratory tests (Table 11), following the timing noted in the SOA (Table 1 and Table 2). All samples should be clearly identified. Sample collection, preparation, and handling/shipment procedures are described in the laboratory manual. For WOCBP, including those who are postmenopausal for less than 12 months, serum pregnancy tests will be performed at initial Screening, and high sensitivity urine pregnancy

tests will be performed at the visits specified in Table 1 and Table 3. Pregnancy tests will be done whenever 1 menstrual cycle is missed during the active treatment period, when potential pregnancy is otherwise suspected, and at the end of the study to confirm the subject has not become pregnant during the study. Pregnancy tests may be repeated per request of institutional review boards (IRBs)/ethics committees (ECs) or if required by local regulations.

Additional laboratory tests may be performed after abnormal findings. Local safety testing as requested by the study team should be entered into the eCRF.

**Table 11 Clinical Laboratory Evaluations**

Type of Evaluation	Tests		
Biochemistry	Albumin Aspartate aminotransferase Alanine aminotransferase Alkaline phosphatase γ-Glutamyl-transferase Lactate dehydrogenase  Total Ig Levels (IgG, IgA, IgM) b	Bilirubin (total) Protein (total) Creatinine and eGFR calculation a Amylase Lipase Total carbon dioxide/serum bicarbonate Blood urea nitrogen Glucose	Sodium Potassium Chloride Calcium Magnesium Phosphate Uric acid
Supplementary LFT visits	Aspartate aminotransferase Alanine aminotransferase Alkaline phosphatase γ-Glutamyl-transferase	Bilirubin (total)	
Hepatic Panel	International normalized ratio Partial thromboplastin time Fibrinogen hsCRP	Hepatitis serology: anti HAV IgG, anti-HAV IgM, HBsAg, anti-HBc, anti HBsAg, anti-HCV, anti-HEV IgG and IgM, anti-VCA IgG and IgM, anti-EA IgG, anti-EBNA IgG, anti-CMV IgG and IgM	Antinuclear antibody, anti-smooth muscle antibody, antibody to liver kidney microsomes Albumin
Hematology	Hematocrit Hemoglobin Red blood cell count Mean corpuscular volume Mean corpuscular hemoglobin Mean corpuscular hemoglobin concentration Reticulocyte count	Platelet count White blood cell count  Flow cytometry for: B cell count b	White blood cell differentials and absolute counts: Basophils Eosinophils Lymphocytes Monocytes Neutrophils
Coagulationb	International normalized ratio Partial thromboplastin time		

Type of Evaluation	Tests		
Urinalysis/ microscopy c and urine chemistry	pH Nitrite Urobilinogen Bilirubin	Glucose Ketone bodies Protein Blood	Microscopy (white blood cells, red blood cells, casts, crystals) Protein/creatinine ratio
Additional urine testing	β-hCG (women only) c		
Other Screening tests d	HCV antibodies Serum β-hCG (women only) Serum β-glucan (Japan only)	HBV antibodies HIV e TSH	FSH HBsAg Quantiferon tuberculosis test
Reflex Testing for HBV DNA	HBV DNA PCR		

β-hCG = Beta-Human Chorionic Gonadotropin, DNA = deoxyribonucleic acid, EA = early antigen, EBNA = Epstein-Barr nuclear antigen, eGFR = Estimated Glomerular Filtration Rate, FSH = Follicle-Stimulating Hormone, HAV = Hepatitis A virus, Hbc = Hepatitis B core antigen, HBsAg = Hepatitis B Surface Antigen, HBV = Hepatitis B Virus, HCV = Hepatitis C Virus, HEV = Hepatitis E virus, HIV = Human Immunodeficiency Virus, hsCRP = high sensitivity C-reactive protein, Ig = Immunoglobulin, MDRD = Modification of Diet In Renal Disease, NK = Natural Killer Cells, PPD = Purified Protein Derivative, TSH = Thyroid Stimulating Hormone, VCA = viral capsid antigen.

- a Calculated using the four-component MDRD equation (Levey 2006).
- b To be done only when specified in Table 1 and not as a standard laboratory evaluation. See Section 7.5.5.2 for details of flow cytometry assessments (safety and exploratory).
- c Urine samples will be collected using a clean catch method. If a female is actively menstruating, urine sample will be delayed and collected preferably within the visit window (but no later than 10 days from the visit). Microscopy will be performed at the central laboratory.
- d Performed only at Screening.
- e HIV testing is to be performed locally and is mandatory for participation in the study.

### 7.4.3.1.1 Immunological Assessments

Absolute values of and changes from Baseline in complement proteins (C3, C4) and anti-dsDNA antibodies may be predictive of disease development and reflective of disease activity and response to therapy in SLE (Bernatsky 2006, Reveille 2004). Total B cell counts and serum Ig levels may change given the mechanism of action of M2951 and are being collected as safety evaluations (see Table 1 and Table 2). These additional immunological assessments will be collected according to the SOA:

- Anti-dsDNA (at Screening, may be measured using 2 assays, 1 of which is a multiplex assay that includes anti-Ro and anti-RNP. Only anti-dsDNA is used to determine subject eligibility and will be reported to the sites.)
- Complement (C3 C4)
- ANA
- C-reactive protein

CCI [REDACTED]

## 7.4.4 Vital Signs, Physical Examinations, and Other Assessments

### 7.4.4.1 Vital Signs

Vital signs, including blood pressure (BP), pulse rate, respiratory rate, weight, and oral temperature will be assessed predose at all study visits (Table 1). Height will be measured at Screening only.

A semiautomated pulse rate and BP recording device with an appropriate cuff size will be utilized. Pulse rate and BP will be measured after 10 minutes rest in the semisupine position with the subject's arm unconstrained by clothing or other material. The BP should be assessed on the same arm for each subject throughout the study.

### 7.4.4.2 Physical Examination

Physical examinations will be assessed as indicated in Table 1 and Table 2.

Physical examination includes assessment of the following: general appearance, skin, head and neck, mouth, lymph nodes, thyroid, abdomen, and nervous, musculoskeletal, cardiovascular, and respiratory systems. Physical examination findings during Screening before obtaining informed consent will be recorded as medical history events and new findings or worsening during the study as AEs.

Abbreviated physical examination should always include assessment of head, ears, eyes, nose, throat, lungs, heart, abdomen, and extremities and other systems as required by symptoms.

Additional assessments (e.g., creatine phosphokinase, ECG, chest radiograph) should be performed as needed to fully obtain information needed for the BILAG 2004 and/or SLEDAI-2K assessments (see Sections 7.3.1 and 7.3.3) if scheduled, as well as to fully evaluate any subject complaints or AEs.

### 7.4.4.3 Resting 12-lead Electrocardiogram and Chest X-ray

A 12-lead ECG will be performed as indicated in Table 1 and Table 2. The 12-lead ECG recordings will be obtained after 10 minutes of rest in a semisupine position.

The following ECG parameters will be obtained directly from the computerized 12-lead ECG recordings: rhythm, ventricular rate, PR interval, QRS duration, and QT interval. The corrected QT interval will be calculated using Fridericia's formula. The overall evaluation (normal/abnormal) will be recorded on the eCRF, and if abnormal, the specific abnormality will be recorded. Abnormal evaluations will be judged as clinically significant or not clinically significant by the Investigator.

The printout of the ECG is to be signed, dated, and filed in the Investigator's Site File along with a signed and dated copy (if the printouts are not on archive-quality paper). In addition, ECGs will also be stored digitally by the Sponsor.

Posteroanterior CXRs will be performed during Screening according to local standard practice. Subjects who had a CXR performed for clinical reasons within three months prior to the Screening Visit do not need to have the CXR repeated. The CXR should show no evidence of active infective process, or any other clinically significant abnormalities. The overall evaluation (normal/abnormal) will be recorded on the eCRF, and if abnormal, the specific abnormality will be recorded. Abnormal evaluations will be judged as clinically significant or not clinically significant by the Investigator.

The 12-lead ECG and CXR will be performed and read locally.

#### **7.4.4.4 Review of Concomitant Medications and Procedures**

Data concerning concomitant medications and procedures will be collected throughout the study. These data will be obtained at scheduled and unscheduled study visits, based on information spontaneously provided by the subject and through questioning of the subject.

Data concerning concomitant medications and procedures may also be obtained from the subject diary, but information thus collected must be reviewed and assessed medically before it is transcribed to the eCRF.

#### **7.4.4.5 Unscheduled Visits**

Unscheduled visits may occur at any time during the study in case of suspected flares or AEs (assessments to be performed according to the Investigator's judgment).

#### **7.4.5 Columbia-Suicide Severity Rating Scale**

The C-SSRS will be used for prospective suicidality assessment. The structured interview prompts recollection of suicidal ideation, including the intensity of the ideation, behavior and attempts with actual/potential lethality.

The scale will be administered by the Treating Investigator or a qualified designee at Screening to identify eligible subjects. It will be self-administered at other time points during the study as per [Table 1](#) and [Table 2](#), using a validated, electronic, self-rated version of the C-SSRS (eC-SSRS) ([Mundt 2010](#), [Mundt 2013](#)).

Subjects who answer "yes" to any suicidal behavior questions or to suicidal ideation questions 4 or 5 on the C-SSRS during the study should be referred for appropriate psychiatric care and the Medical Monitor notified.

Please note that assessing the risk of suicide is a difficult and complex task when applied to the individual subject. No single clinical scale can replace a thorough medical examination and suicide risk assessment. Ultimately, the determination of the presence of suicidality depends on clinical judgment.

## 7.5

## Exploratory Assessments

CCI

CCI

CCI

CCI

CCI

CCI

CCI

CCI

CCI

CCI

CCI

CCI

CCI

## 8 Statistics

### 8.1 Sample Size

A sample size of 103 evaluable subjects per group provides 80% power at the  $\alpha = 0.025$  one-sided significance level to detect

- an absolute improvement of 20% in Week 52 SRI-4 response proportion for M2951-treated subjects relative to placebo-exposed subjects, among subjects with SLEDAI-2K total score  $\geq 6$  at Screening, assuming a placebo response proportion of 40%,

or

- an absolute improvement of 25% in Week 52 SRI-6 response proportion for M2951-treated subjects relative to placebo-exposed subjects, among subjects with SLEDAI-2K total score  $\geq 10$  at Screening (i.e., HDA), assuming a placebo response proportion of 30%,

assuming that each co-primary endpoint is tested via a chi-squared test of the odds ratio (OR) for treatment effect at the 0.0125 one-sided level, and assuming that approximately 50% of randomized subjects are in the HDA group. If the absolute improvement in Week 52 SRI-6 response proportion in HDA subjects is only 20%, the power is 76%. Approximately 108 subjects will be randomized per treatment group to protect against a loss of information due to drop-out (for reasons other than efficacy/safety) of 5% over 52 weeks. Given the randomization ratio 1:1:1:1, the total sample size required for the primary analysis is planned to be 432 subjects.

Approximately 432 subjects will enter the main study. Assuming an 80% rate of continuation to LTE, approximately 346 subjects are expected to enter the LTE Period.

The Japan cohort size was determined to provide a reliable evaluation of consistency in the Week 52 SRI-4 response proportion between the non-Japan and Japan regions. Assuming that:

- (i) the Week 52 SRI-4 response proportion in the placebo group is 0.40 for both the non-Japan and Japan regions,
- (ii) the Week 52 SRI-4 response proportion due to each of the 3 M2951 dose groups is 0.60 for both regions, so that the true underlying effect size is 0.20 for both regions,
- (iii) a total evaluable sample size of 412 (i.e., 309:103 randomization for M2951: placebo) is involved in analysis of the two regions,

and applying “Method 2” from the PMDA Guidance, 32 evaluable subjects in the Japan cohort are required so that both observed region-specific effect sizes exceed 0.04 with probability of 80%. Taking into account a loss of information due to 5% drop-out at Week 52, for reasons unrelated to efficacy or safety, the total number of Japan subjects to be randomized is 36, or 8.3% of the total planned enrollment of 432.

If enrollment of Japanese subjects is slow, then the entire Japanese cohort will not be part of the primary analysis cohort. A maximum of  $n = 36$  Japanese subjects will be analyzed for Week 52 SRI-4 at a time point after the primary analysis for the purpose of assessing consistency. Therefore, the total enrollment will range from  $n = 432$  to 468, where  $468 = 432 + 36$  is the number enrolled if none of the 36 Japanese subjects enroll in time to be included in the primary analysis. The number of subjects enrolled per group will range from  $n = 108$  to 117.

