## Statistical Methods

There will be at least two planned analyses in this study - the primary and final analyses. There may be up to four planned analyses, depending on whether the optional futility interim analysis (IA) is conducted, and whether the analysis for treatment effect consistency is coincident with the primary analysis, or is conducted after the primary analysis.

If the futility IA is conducted, it will be based on Week 24 SRI-4 response among all subjects in the primary analysis cohort and Week 24 SRI-6 response among HDA subjects in the primary analysis cohort. The IA will be conducted when 100% of subjects in the primary analysis cohort, reach Week 24 of treatment or prematurely discontinue from treatment prior to Week 24. If the response proportion difference for both co-primary endpoints is sufficiently low at Week 24, as defined in the Integrated Analysis Plan (IAP), consideration will be given to termination of the study. If enrollment is slower than expected, consideration will be given to conducting the interim futility analysis when the first 50% of the primary analysis cohort reach Week 24 of treatment, or prematurely discontinue from treatment. An IDMC will monitor safety and tolerability as well as review the data from the IA. The IA will be prepared by a team independent of the study teams (Sponsor and PPD).

The primary analysis cohort consists of the first 432 subjects randomized. However, if drop-out for reasons unrelated to efficacy or safety is higher than expected, effectively reducing the power of the study, the IAP may prespecify that the primary analysis cohort may include all subjects randomized. The primary analysis will be based on Week 52 SRI-4 response among all subjects in the primary analysis cohort, and Week 52 SRI-6 response among HDA subjects in the primary analysis cohort. This analysis is triggered when 100% of subjects in the primary analysis cohort:

- Complete Week 52 of treatment and either enter LTE or complete Safety Follow-Up, or

- Prematurely discontinue from treatment prior to Week 52 and complete Safety Follow-Up, or
- Prematurely discontinue from study without Safety Follow-Up.

The Japanese cohort may be fully, partially, or not included in this primary analysis, depending on the enrollment rate. The primary analysis will be performed by PPD staff when the primary analysis trigger condition has been met, protocol violations determined, and the database is locked for the primary analysis.

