## 8.5.2 Analysis of Primary Endpoints

The primary analysis of SRI-4 response at Week 52 among all subjects in the primary analysis cohort, and SRI-6 response at Week 52 among HDA subjects in the primary analysis cohort, will be an estimate of OR, together with associated two-sided 95% CI and p-value (testing null hypothesis  $H_0: OR = 1.0$ ), comparing each M2951 dose group to placebo, based on a logistic model for the odds of a given SRI response in the appropriate population, with M2951 dose group or placebo group as a factor and adjustment for covariates based on randomization strata. Additional covariates may be included in the model as specified in the IAP. In the primary analysis of SRI-4 or SRI-6 response at Week 52, a subject experiencing flare or CS dose increase during Weeks 41 to 52, or a subject with a missing response at Week 52, will be considered a non-responder.

The primary analysis of the co-primary efficacy endpoints will be based on the mITT analysis set, with supportive analyses based on the ITT and PP analysis sets, if the size of these analysis sets differ substantially ( $> 10\%$ ) from the size of the mITT analysis set.

The Family-Wise type 1 error rate (FWER) due to the co-primary endpoints and multiple M2951 dose group comparisons versus placebo will be controlled at the two-sided  $\alpha = 0.05$  level via a tree

gatekeeping procedure. The four hypotheses associated with the comparisons involving the co-primary endpoints and the two highest dose groups will form the first family of hypotheses in the tree. This family will be tested via the truncated Hochberg procedure, with truncation fraction pre-specified in the IAP. The multiple-testing procedure for the remainder of the tree, including the hypotheses associated with the comparisons involving the co-primary endpoints and the lowest dose group will be specified in the IAP.

A test for monotonic dose-response relationship, between ordered M2951 dose and SRI-4 response OR relative to placebo, will be performed as a supportive analysis. Similarly, a test for monotonic dose-response relationship, between ordered M2951 dose and SRI-6 response OR relative to placebo, will be performed as a supportive analysis in the HDA subgroup.

Descriptive statistics for SRI-4 response, and for SRI-6 response in the HDA subgroup, will be provided for each treatment group by time point.

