Updates were made to the analysis cohort.	Synopsis, 8.5.2 Analysis of Primary Endpoints	23, 110	Analysis of Co-primary Efficacy Endpoints The primary analysis of SRI-4 response at Week 52 among all subjects in the n = 432 cohort, and SRI-6 response at Week 52 among HDA subjects in the n = 432 cohort, will be an estimate of OR, together with associated two-sided 97.5% CI and p-value, comparing each M2951 dose group to placebo, based on a logistic model for the odds of a given SRI response in the appropriate population, with M2951 dose group or placebo group as a factor and adjustment for covariates based on randomization strata.	Analysis of Co-primary Efficacy Endpoints The primary analysis of SRI-4 response at Week 52 among all subjects in the primary analysis n = <del>432</del> cohort, and SRI-6 response at Week 52 among HDA subjects in the n = <del>432</del> primary analysis cohort, will be an estimate of OR, together with associated two sided <del>957.5%</del> CI and p-value ( testing null hypothesis H0: OR = 1.0 ), comparing each M2951 dose group to placebo, based on a logistic model for the odds of a given SRI response in the appropriate population, with M2951 dose group or placebo group as a factor and adjustment for covariates based on randomization strata.	Drop-out rates unrelated to efficacy or safety are higher than anticipated.

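### Section 8.1 still sizes the trial for 5% drop-out unrelated to efficacy or safety, although Version 7.0 itself says such drop-out is higher; the printed 80%/76% power has no reserve above 5%

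*Protocol*

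**What the plan says.** Protocol 8.1 (repeated in the Synopsis, Statistical Methods) opens its sizing with "A sample size of 103 evaluable subjects per group provides 80% power at the" one-sided 0.025 level. The target is "an absolute improvement of 20% in Week 52 SRI-4 response proportion for M2951-treated subjects relative to placebo-exposed subjects" from a placebo rate of 40%, or a 25-point gain in SRI-6 among high-disease-activity (HDA) subjects from 30%. Each endpoint is "tested via a chi-squared test of the odds ratio (OR) for treatment effect at the 0.0125 one-sided level", with half the subjects HDA. If the HDA gain is only 20 points, the printed power is 76%. The step from 103 to 108 per group (432 in total) is there "to protect against a loss of information due to drop-out (for reasons other than efficacy/safety) of 5% over 52 weeks". Total enrolment is fixed at 432 to 468; the upper figure "is the number enrolled if none of the 36 Japanese subjects enroll in time to be included in the primary analysis".

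Four other places bear on this.

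- **Appendix V, Amendment 14 (Version 7.0).** The reason given for the changes to the primary analysis cohort (Synopsis and 8.5.2), to 5.5.1 and to 8.6 is "Drop-out rates unrelated to efficacy or safety are higher than anticipated".
- **8.3.1 and 8.5.2.** SRI response requires that the investigational product was not discontinued, "or a subject with a missing response at Week 52, will be considered a non-responder".
- **5.1, Statistical Methods.** If such drop-out exceeds expectation, "the IAP may prespecify that the primary analysis cohort may include all subjects randomized" instead of the first 432.
- **5.5.1.** Higher enrolment will be considered to offset withdrawals unrelated to safety or efficacy. No number is given.

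**The concern.** Two things do not fit together in the current version. First, 8.1 rests on a 5% input that the same version reports as exceeded. The rationale column explains text now in force, so this is not a comparison with superseded wording. The amendment also edited 8.1, to add the expected extension numbers, and left 5%, 108 and 80%/76% standing.

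Second, the allowance in 8.1 is framed as loss of evaluable subjects, that is, removal from the analysis. The primary analysis instead keeps most drop-outs as failures, so both response rates and their difference shrink. That costs more power per drop-out than removal does.

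At stake are the figure against which a negative result would be read and the sponsor's decision under 5.5.1 on whether to enlarge the trial.

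**Working it through.** **Inputs (8.1).** SRI-4 0.40 v 0.60 in all subjects. SRI-6 0.30 v 0.55 (or 0.50) in the HDA half. One-sided 0.0125 per endpoint, so the critical value is 2.241. Success means at least one endpoint significant for one dose against placebo.

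**Assumptions added.** Equal drop-out in both arms; SRI-6 responders are also SRI-4 responders; the SRI-4 rate is the same in HDA and other subjects.

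**Formula for one endpoint.** Power = Φ[(D − 2.241·s0)/s1], where D = p1 − p0, s0 = √[2p̄(1−p̄)/n] and s1 = √{[p0(1−p0) + p1(1−p1)]/n}. The chance of winning at least one endpoint follows from the joint distribution of the two tests, whose correlation under nesting is about 0.6. It was calculated by bivariate normal and by simulation.

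**Step 1: the plan's own figure.** At n = 103, SRI-4: s0 = √(0.50/103) = 0.0697 and s1 = √(0.48/103) = 0.0683. Power = Φ[(0.20 − 0.1562)/0.0683] = 74.0%. SRI-6 with about 51.5 per arm gives about 63% (43% for the 20-point gain). At least one: 81.6%/77.2% by simulation and 82.1%/78.0% by bivariate normal. The printed 80%/76% reproduce. The inflation also checks: 103/0.95 = 108.4.

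**Step 2: drop-outs as non-responders.** With drop-out d, every rate is multiplied by (1 − d) and n stays at the number randomized. For SRI-4 at 108 per group and d = 10%, the rates are 0.36 v 0.54, so D = 0.18, s0 = √(0.495/108) = 0.0677 and s1 = √(0.4788/108) = 0.0666. Power = Φ[(0.18 − 0.1517)/0.0666] = 66.4%, against 71.4% at d = 5%.

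**Step 3: two readings of the planned rates.** The protocol does not say whether 40% and 30% already count drop-outs as failures. If they exclude drop-outs, the factor is (1 − d). If they already include 5%, the factor is (1 − d)/0.95, for example 0.90/0.95 = 0.947 at 10%.

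Power to win at least one endpoint, for a 25-point / 20-point HDA gain:

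| Drop-out | 108 per group, rates exclude drop-out | 108 per group, rates include 5% | 117 per group, rates exclude drop-out |
|---|---|---|---|
| 5% | 80% / 76% | 84% / 80% | 83% / 79% |
| 10% | 76% / 71% | 80% / 75% | 80% / 75% |
| 15% | 71% / 66% | 75% / 70% | 76% / 71% |
| 20% | 67% / 62% | 71% / 66% | 71% / 66% |

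Simulation and the normal approximation agree to within about one point. The 10% to 20% rows are an assumed range, because the documents state no observed rate.

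**Step 4: what the non-responder rule contributes.** If 10% were simply removed (108 × 0.90 = 97.2 per group), power would be 79.8%/75.4% by bivariate normal. Most of the loss at 10% in the first column therefore comes from dilution, not from the smaller number.

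**Step 5: what widening the cohort adds.** Within 8.1's range, the subjects beyond the first 432 number 468 − 432 = 36 at most, or 9 per group, and they are there only because Japanese subjects enrolled late. If the Japanese cohort enrols on time, the addition is 0. On the first reading, keeping 80% needs about 119 per group (476 in total) at 10% drop-out, 132 (528) at 15% and 146 (584) at 20%. All exceed 468.

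**The case against.** The best defence is that no printed figure is wrong. The 80%/76% are stated for 103 evaluable subjects and reproduce, and 108 per group still delivers them at 5% drop-out under the non-responder rule. That stands. A reader might infer that the arithmetic of 8.1 is faulty or that the power has already been lost. The documents support neither: what is out of date is a planning input, and the size of the excess is unknown. At 6% the loss on the first reading is about one point.

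It can also be said that a Week 52 SRI rate may already treat discontinuation as failure, since that is part of the SRI definition. On that reading, 10% drop-out leaves power at about 80%/75%. This also stands, and it is why both readings are shown; a shortfall remains at 15% and 20%.

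A reader might conclude that the remedies are worthless because more subjects cannot undo dilution. That goes too far. At 117 per group and 10% drop-out, power is back to about 80%/75%, and larger samples restore it fully. Nor does widening the cohort necessarily add nobody: read with 5.5.1, extra subjects could be enrolled and then counted. What remains is that 5.5.1 gives no number and 8.1 keeps a range that leaves no room for it.

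Nor was drop-out the main reason for the amendment. Appendix V names the long-term extension as the major reason; drop-out is the reason for three change rows, and the wording in 5.1 is conditional.

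Finally, dilution is not total. Subjects with no post-Baseline assessment leave the mITT set and reduce n instead, and 8.5.1 plans a sensitivity analysis that uses available data for drop-outs unrelated to efficacy or safety. Neither changes the primary analysis for the other drop-outs.

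**Conclusion.** The point holds as an inconsistency within Version 7.0. Section 8.1 and the Synopsis keep 5%, 108 per group and 432 to 468 in total, while the same version states that drop-out of this kind is running above expectation. The printed power is correct up to about 5% and has no reserve beyond it if the planned rates exclude drop-outs. If they already include 5%, there is reserve to about 10% and none further. Over the assumed 10% to 20%, the shortfall at 108 per group is about 4 to 14 points on the first reading and 0 to 10 points on the second. These figures rest on equal drop-out across arms, nested SRI-6 and SRI-4 responses, and an HDA share of 50%. Separately, the fixed enrolment range in 8.1 does not fit the extra enrolment contemplated in 5.5.1, and without that enrolment the wider cohort in 5.1 adds between 0 and 36 subjects for reasons unrelated to drop-out.

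**What to change.** In 8.1 and the Synopsis:

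1. Replace 5% with the current blinded pooled rate of drop-out unrelated to efficacy or safety.
2. State whether the planned 40% and 30% placebo rates, and the rates assumed on treatment, already count drop-outs as non-responders.
3. Restate the power for 108 and 117 randomized per group under the non-responder rule.
4. Reconcile the 432 to 468 range with the possible extra enrolment in 5.5.1 and with the cohort wording in 5.1, so that it is clear which subjects a widened cohort would contain.

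The cost is wording plus a short recalculation from blinded data. No extra patients are required by this change. The downside is a less favourable stated power, which is the figure that any decision to enlarge the trial should use.
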